7.2 General Concomitant Medication and Supportive Care Guidelines

The following are permitted therapies while receiving investigational agents.

- Oral contraceptives
- Hormone-replacement therapy
- Been stable on anticoagulation therapy (at a stable dose or low-molecular-weight heparin) that was initiated at least two months prior to initiation of study treatment.
- Inactivated influenza vaccinations
- Mineralocorticoids (e.g., fludrocortisone)
- Inhaled corticosteroids administered for chronic obstructive pulmonary disease or asthma
- Low-dose corticosteroids administered for orthostatic hypotension or adrenocortical

Columbia University Irving Medical Center
Herbert Irving Comprehensive Cancer Center
AAAS4165_Version Date: 07/07/2021

insufficiency amounting to less than 10mg of prednisone daily, and with the approval of the Principal Investigator.

- Hormonal therapy with gonadotropin-releasing hormone agonists or antagonists for prostate cancer
- Nerve blocks for pain control with adequate pain management

7.2.1 Medications to be given with precaution due to effects related to cytochrome P450 enzymes

Concomitant treatment is permitted if the medication is not expected to interfere with the evaluation of safety or efficacy of the study drug. During the study, if the use of any concomitant treatment becomes necessary (e.g., for treatment of an adverse event), the treatment must be recorded on the eCRF, including the reason for treatment, generic name of the drug, dosage, route, and start and stop dates of administration.

Concomitant use of strong and **moderate inhibitors of CYP3A** (e.g., clarithromycin, itraconazole, ketoconazole, posaconazole, telithromycin, and voriconazole; see Appendix 2) should be avoided during cobimetinib treatment because cobimetinib is a sensitive substrate of CYP3A, and exposures will be increased in the presence of these agents (approximately 7-fold increase in presence of itraconazole in healthy subjects). Consumption of grapefruit juice, a potent CYP3A4 enzyme inhibitor, is prohibited during the study and for 30 days after the last dose of study treatment.

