8.2 Drug-specific dose delays/modifications

8.2.1 Dose modifications: Atezolizumab

There will be no dose modifications for atezolizumab in this study. Atezolizumab treatment may be temporarily suspended in patients experiencing toxicity considered to be related to study treatment. If corticosteroids are initiated for treatment of the toxicity, they must be tapered over ≥ 1 month to ≤ 10 mg/day oral prednisone or equivalent before atezolizumab can be resumed. If atezolizumab is withheld for >105 days, the patient will be discontinued from atezolizumab. However, atezolizumab may be withheld for >105 days to allow for patients to taper off corticosteroids prior to resuming treatment. Atezolizumab can be resumed after being withheld for >105 days if the Principal Investigator agrees that the patient is likely to derive clinical benefit. Toxicities associated or possibly associated with atezolizumab treatment should be managed according to standard medical practice. Additional tests, such as autoimmune serology or biopsies, should be used to evaluate for a possible immunogenic etiology. Although most immune-related adverse events observed with immunomodulatory agents have been mild and self-limiting, such events should be recognized early and treated promptly to avoid potential major complications. Discontinuation of atezolizumab may not have an immediate therapeutic effect, and in severe cases, immune-related toxicities may require acute management with topical corticosteroids, systemic corticosteroids, or other immunosuppressive agents. The investigator should consider the benefit-risk balance a given patient may be experiencing prior to further administration of atezolizumab. In patients who have met the criteria for permanent discontinuation, resumption of atezolizumab may be considered if the patient is deriving benefit and has fully recovered from the

immune related event. Patients can be re-challenged with atezolizumab only after approval has been documented by both, the Investigator (or an appropriate delegate) and the Principal Investigator. Please refer to Appendix 1 for management of atezolizumab-related adverse events.

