8.3.1 Cobimetinib-associated adverse events

For specific guidelines on how to respond to adverse events associated with cobimetinib, see Appendix 1.

The following adverse events are classified as identified risks associated with cobimetinib: serious retinopathy, left ventricular dysfunction, severe hemorrhage, rhabdomyolysis, and pneumonitis. The following adverse events are classified as potential risks for cobimetinib: severe hepatotoxicity (Grade ≥ 3), impaired female fertility, and teratogenicity and developmental toxicity. In addition, there is the possibility of drug-drug interactions in patients treated with cobimetinib. Clinical and safety data were reported that included monotherapy and combination

studies, of which key adverse events are summarized here, but for a complete review of the safety data please refer to the most current IB version.

Common (>10%) adverse events observed with Cobimetinib included bleeding, serious retinopathy, diarrhea, nausea, emesis, rash, pyrexia, chills, anemia, increased liver function enzymes, increased creatinine phosphokinase, and photosensitivity. Less common (1% - 10%) adverse events included decreased left ventricular ejection, risk of basal and squamous cell carcinoma, kertocanthoma, dehydration, hyponatremia, hypophosphatemia, hyperglycemia, and pneumonitis. Guidelines for treatment interruption or discontinuation in the case of adverse events are described in Appendix 1.

Cobimetinib should be permanently discontinued for:

- Grade 4 hemorrhage events attributed to cobimetinib
- Symptomatic or asymptomatic decrease of LVEF < 40% or $\geq 10\%$ absolute decrease from baseline after treatment break or recurrent symptomatic absolute decrease of LVEF < 10% (See Table 1 for details)
- Rhabdomyolysis or symptomatic CPK elevations not improving within 4 weeks of dose interruption
- Liver laboratory abnormalities not resolving to Grade ≤ 1 within 4 weeks of dose interruption or if Grade 4 liver laboratory abnormalities recur after initial improvement
- QTc increase meets values of both > 500 ms and > 60 ms change from pre-treatment values or 3rd occurrence of QTc > 500 ms during treatment and change from pre-treatment value remains ≤ 60 ms

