| AST/ALT > 10 x ULN | 
 • Permanently discontinue atezolizumab (if applicable), cobimetinib, and hydroxychloroquine and contact PI. • Monitor LFTs every 48-72 hrs until decreasing; then monitor weekly. • Refer to hepatologist and consider liver biopsy. • If Received atezolizumab – 
 • Consider initiating 1-2 mg/kg.day oral prednisone treatment (or equivalent). • If corticosteroids are initiated and event does not improve within 48 hrs, consider adding immunosuppressive agent. • If event resolves to $AST/ALT \leq 3 \times ULN$ with total bilirubin $\leq 2 \times ULN$, |

Columbia University Irving Medical Center
Herbert Irving Comprehensive Cancer Center
AAAS4165_Version Date: 07/07/2021

| | |
|---|--|
| | taper corticosteroids over ≥ 1 month. |
| LFT = liver function test; ULN = upper limit of normal. ^a Corticosteroids must be tapered over ≥ 1 month to ≤ 10 mg/kg/day oral prednisone or equivalent before atezolizumab may be resumed. ^b Atezolizumab may be withheld for more than 12 weeks to allow for corticosteroid treatment tapering. Course must be agreed upon by the investigator and PI. ^c Resuming atezolizumab may be considered in patients who are deriving benefit and have fully recovered from the immune-related event. Patients can be re-challenged with atezolizumab only after approval from both the investigator and the PI. | |

Table A1.5. Guidelines for managing pulmonary events in response to **atezolizumab, and/or cobimetinib.**

| Event | Action |
|------------------|--|
| General guidance | 
 • All pulmonary events would be thoroughly evaluated for other commonly reported etiologies. |
| Grade 1 | 
 • Continue atezolizumab (if applicable) and cobimetinib. • Re-evaluate on serial imaging; • Consider referral to pulmonary specialist; |
| Grade 2 | 
 • Withhold atezolizumab (if applicable) and cobimetinib. • Refer patient to pulmonary and infectious disease specialist; • Consider bronchoscopy or BAL; • If results are consistent with immune-related etiology or pneumonitis, initiate treatment with 1-2 mg/kg/day oral prednisone or equivalent; • Resume atezolizumab (if applicable) at fixed dose if event resolves to Grade 1 or better within 12 weeks; |

Columbia University Irving Medical Center
Herbert Irving Comprehensive Cancer Center
AAAS4165_Version Date: 07/07/2021

| | |

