| ^c Resuming atezolizumab may be considered in patients who are deriving benefit and have fully recovered from the immune-related event. Patients can be re-challenged with atezolizumab only after approval from both the investigator and the PI. | |

Table A1.7. Guidelines for managing pancreatic events in response to *atezolizumab, and/or cobimetinib*.

| Event | Action |
|---|--|
| Amylase and/or lipase elevation Grade 1 | 
 • Continue atezolizumab (if applicable) and cobimetinib. • Monitor amylase and lipase prior to dosing. |
| Amylase and/or lipase elevation Grade 2 | 
 • Continue atezolizumab (if applicable) and cobimetinib. • Monitor amylase and lipase weekly. • For prolonged elevation (> 3 weeks), consider 10 mg/day oral prednisone or equivalent. |
| Amylase and/or lipase elevation, Grade 3 or 4 | 
 • Withhold atezolizumab (if applicable). • Continue cobimetinib. |

Columbia University Irving Medical Center
Herbert Irving Comprehensive Cancer Center
AAAS4165_Version Date: 07/07/2021

| | |
|-------------------------------------|---|
| | 
 • Monitor amylase and lipase every other day. • If Received atezolizumab – 
 • If no improvement, consult GI and consider 1-2 mg/kg/day oral prednisone or equivalent. • Resume atezolizumab if event resolves to Grade 1 or better within 12 weeks. ^{a,b} • Permanently discontinue atezolizumab and contact PI if event does not resolve to Grade 1 or better within 12 weeks. ^{a,b,c} • For recurrent events, permanently discontinue cobimetinib, and contact PI. |
| Immune-related pancreatitis Grade 2 | 
 • Withhold atezolizumab (if applicable). • Continue cobimetinib. • Refer patient to GI specialist. • If Received atezolizumab – 
 • Upon improvement, initiate 1-2 mg/kg/day IV methylprednisolone or equivalent. Convert to 1-2 mg/kg/day oral prednisone upon improvement. • Resume atezolizumab if event resolves to Grade 1 or better within 12 weeks. ^{a,b} • Permanently discontinue atezolizumab and contact PI if event does not resolve to Grade 1 or better within 12 weeks. ^{a,b,c} • For recurrent events, permanently discontinue atezolizumab, and contact PI. |
| Immune-related pancreatitis Grade 3 | 
 • Withhold cobimetinib. |

Columbia University Irving Medical Center

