^a Resuming atezolizumab may be considered in patients who are deriving benefit and have fully recovered from the immune-related event. Patients can be re-challenged with atezolizumab only

Table A1.12. Guidelines for managing electrocardiogram QT corrected interval prolonged in response to *atezolizumab, cobimetinib, and/or hydroxychloroquine*.

| Event | Action |
|--|--|
| QTc > 500ms and change from pre-treatment value remains $\leq 60\text{ms}$ | |
| 1st Occurrence | Temporarily interrupt treatment until QTc decreases below 500 ms; reduce Cobimetinib by 1 dose level |
| 2nd Occurrence | Temporarily interrupt treatment until QTc decreases below 500 ms; reduce Hydroxychloroquine by 1 dose level |
| 3rd Occurrence grade 3 | Temporarily interrupt treatment until QTc decreases below 500 ms; reduce Cobimetinib and Hydroxychloroquine by 1 more dose level |
| Grade 4 Torsade de pointes; polymorphic ventricular tachycardia; signs/symptoms of serious arrhythmia | Permanently discontinue study drugs |
| QTc increase meets values of both $> 500\text{ ms}$ and $> 60\text{ ms}$ change from pre-treatment values | |
| 1st Occurrence | Discontinue drugs permanently |

Drugs should be interrupted for 3 ± 2 days and Electrocardiogram repeated until QTc below 500ms for four attempts. Subject should be referred to an electro cardiologist if QTc does not decrease below 500ms after study drug held for greater than 7 days (consecutively).

Table A1.13. Guidelines for managing rhabdomyolysis or CPK elevation in response to *atezolizumab, cobimetinib, and/or hydroxychloroquine*.

| Event | Action |
|---|---|
| Rhabdomyolysis or CPK elevation | |
| General guidance | 
 • Evaluate for cardiac cause (check ECG, serum cardiac troponin, and CPK-isoforms M and B fraction) and rhabdomyolysis (clinical examination; serum creatinine, potassium, calcium, phosphorus, uric acid, and albumin; and urine myoglobin). • Assess patient for any history of strenuous physical activity, blunt trauma, or recent IM injections. |
| Asymptomatic CPK elevation, Grade 1, 2, or 3 | 
 • Continue study drugs. • Recheck CPK at least once a week. |

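### Appendix 1 prints the steroid limit for restarting atezolizumab in mg/kg/day instead of mg/day; the third-QTc rule and cobimetinib Table 6 need smaller corrections

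*Combined protocol and SAP*

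**What the plan says.** **Steroid limit.** Section 8.2.1 says that when steroids have been given for toxicity, "they must be tapered over ≥ 1 month to ≤ 10 mg/day oral prednisone or equivalent before atezolizumab can be resumed". It then directs sites onward: "Please refer to Appendix 1 for management of atezolizumab-related adverse events". In Appendix 1, footnote a under Tables A1.4, A1.5, A1.6, A1.7 and A1.9 reads "Corticosteroids must be tapered over ≥ 1 month to ≤ 10 mg/kg/day oral prednisone" or equivalent. Elsewhere the protocol expresses low-dose steroid use per day. Section 7.2 permits low-dose steroids for certain conditions "amounting to less than 10mg of prednisone daily", and Table A1.7, for prolonged grade 2 enzyme elevation, says "consider 10 mg/day oral prednisone or equivalent".

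**Third QTc event.** Section 8.3.1 lists the reasons to stop cobimetinib permanently. One is "3rd occurrence of QTc > 500 ms during treatment and change from pre-treatment value remains" at or below 60 ms. The same section adds: "Guidelines for treatment interruption or discontinuation in the case of adverse events are described in Appendix 1". For that same third event, Table A1.12 says to interrupt treatment until QTc falls below 500 ms and then "reduce Cobimetinib and Hydroxychloroquine by 1 more dose level".

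**Cobimetinib reductions.** Table 6 in Section 8.2.2 gives level -1 as 40 mg and level -2 as 20 mg, with no reference to the starting dose. Dose levels 1 and 2 start at 40 mg (Section 4.1.1, Table 1). Section 8.2.2 equates one dose level with 20 mg when it describes re-escalation. Section 8.2.4 sends sites to Tables 6 and 7 and to Appendix 1, and requires cobimetinib to stop if a further reduction is needed after two.

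**The concern.** These are working safety instructions. They decide when a checkpoint inhibitor restarts after immune toxicity and how much cobimetinib a patient takes after an adverse event. Sections 8.2.1, 8.2.4 and 8.3.1 all send sites to Appendix 1, and no rule says which text prevails when the body and the appendix differ. The protocol provides for affiliate sites, so two sites could manage the same patient differently and each could point to the protocol in support.

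The steroid unit is the main point, because the printed number is simply wrong as a limit. The other two are secondary: a conflict that arises rarely, and a table that is ambiguous for one starting dose.

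**Working it through.** No sample-size or power figure is involved. The check sets the texts side by side and does the dose arithmetic.

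**1. Steroid limit**
- Inputs: 10 mg/day (Section 8.2.1); 10 mg/kg/day (footnote a); treatment dose 1-2 mg/kg/day (footnoted rows of Tables A1.4, A1.5 and A1.7).
- Printed limit divided by treatment dose: 10 / 2 = 5 and 10 / 1 = 10. A patient on full treatment dose is already below the printed number.
- The protocol gives no weight distribution. At assumed weights of 50, 70 and 90 kg, 10 mg/kg/day is 500, 700 and 900 mg/day, or 50, 70 and 90 times the Section 8.2.1 limit.
- Reach: in Table A1.6 no row carries the marker in the text available, and the marked row of Table A1.9 uses topical steroids. In those two tables the footnote disagrees with Section 8.2.1 but governs no stated systemic dose. Dose level 1 has no atezolizumab, so the limit does not arise there.

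**2. Third QTc event**
- QTc above 500 ms with a change of at most 60 ms requires a baseline above 500 - 60 = 440 ms. Exclusion 22 removes men at 450 ms or more and women at 470 ms or more. That leaves baselines between 440 and 450 ms (men) and between 440 and 470 ms (women), assuming the same correction formula throughout.
- Table A1.12 reduces cobimetinib at the first and third events:

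| Starting dose and reading | After 1st event | After 3rd event, Table A1.12 | After 3rd event, Section 8.3.1 |
|---|---|---|---|
| 60 mg | 40 mg | 20 mg | 0 mg |
| 40 mg, 20 mg steps | 20 mg | 0 mg | 0 mg |
| 40 mg, Table 6 read literally | 40 mg | 20 mg | 0 mg |

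- Hydroxychloroquine is reduced at the second and third events: 1200 to 1000 to 800 mg/day (Table 7). Section 8.3.1 has no competing rule for it.
- A confirmed QTc of 501 ms or more in the first 28 days is already a DLT criterion (Section 4.1.1.1), and Section 8.1 removes DLT patients unless they are benefiting. Three such events would therefore mostly fall after cycle 1.

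**3. Table 6 for a 40 mg starter**
- Read literally: 40 to 40 to 20 mg, so the first step is 40 - 40 = 0 mg. Read as 20 mg steps: 40 to 20 to 0 mg, so one reduction is available before stopping, not two.
- Rows ordering a one-level cobimetinib reduction: A1.2 (1), A1.3 (1), A1.4 (1), A1.6 (1), A1.9 (1), A1.10 (4), A1.11 (1), A1.12 (2), A1.13 (2). The total is 14 rows in 9 of the 15 tables. Two CPK events appear in both A1.10 and A1.13, so 14 - 2 = 12 distinct events.
- Average patients starting at 40 mg, from Table 2 (dose levels 1 + 2, of 18): 11 + 4 = 15, 6 + 6 = 12 and 2 + 5 = 7 in scenarios 1 to 3. This is exposure to the ambiguity, not a count of patients affected.
- Link to the primary endpoint: Section 4.1.1.1 makes any circumstance leading to a dose reduction in the first 28 days a DLT criterion. For a 40 mg starter, a one-level step is no change under the literal table and a 20 mg reduction under 20 mg steps. Section 8.1 bars reductions in that window unless a DLT is confirmed, which limits the cases. Classification of an event that qualifies on no other ground could still turn on the reading.

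**The case against.** The best defence of the steroid footnote is that the protocol has other protections. Section 8.2.1 is mandatory, the footnote keeps the taper of at least one month, and a patient at 10 mg/day or less satisfies both texts. The Principal Investigator must also agree to holds beyond 12 weeks and to re-challenge. This stands in part. A reader might infer that the appendix lets atezolizumab restart at full steroid dose with no taper, and the documents do not support that. What remains is that the appendix states no usable endpoint for the taper, and Section 8.2.1 itself sends sites there. The Principal Investigator provisions do not cover an ordinary restart within 12 weeks.

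On QTc, the case is narrow and Section 8.3.1 states the stricter rule outright. That is right, and under 20 mg steps the two rules agree for 40 mg starters. For a 60 mg starter both cannot be followed. Which to keep is a clinical decision.

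On Table 6, a reader might infer two flatly opposed rules. The documents do not go that far. The 20 mg level size in Section 8.2.2 lets a careful site infer 40 to 20 mg, and calling an unchanged dose a reduction would be odd. The limit in Section 8.2.4 can also be read as a ceiling rather than a promise of two steps. Tablets are 20 mg and must not be cut (Section 7.1.2), so 20 mg is the practical floor. This is an ambiguity to remove.

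**Conclusion.** The steroid footnote is wrong as written in five tables. Its limit is 5 to 10 times the treatment dose in the footnoted rows of Tables A1.4, A1.5 and A1.7, whatever the body weight, and so never binds there. It must be corrected, although Section 8.2.1 and the minimum taper still protect patients at sites that read both texts.

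The QTc conflict is real but rare. It gives 0 or 20 mg of cobimetinib for a 60 mg starter with no other reductions. The Table 6 problem reaches more patients but is an ambiguity. The documents give no reduction rate for a 40 mg regimen, so the number affected cannot be estimated.

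Sample size and planned error rates are unaffected. A reader might conclude that the MTD estimate is equally untouched, since these look like management rules only. The documents do not support that assurance, because dose reduction is tied to the DLT definition. Nor do they show that the estimate would be biased; the effect on DLT classification is possible and unquantified.

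**What to change.** 1. **Steroid limit (main).** In footnote a of Tables A1.4, A1.5, A1.6, A1.7 and A1.9, replace mg/kg/day with mg/day, so that the limit matches Section 8.2.1.
2. **Third QTc event.** Align the third-occurrence row of Table A1.12 with the stricter Section 8.3.1 rule: interrupt until QTc is below 500 ms, stop cobimetinib permanently, and lower hydroxychloroquine by one further level. This is subject to the sponsor's medical lead, who may document a different choice and amend Section 8.3.1 to match. Note in the row that stopping cobimetinib at dose level 1 leaves hydroxychloroquine alone, and that under Section 8.2.4 such a patient continues only with Principal Investigator approval.
3. **Cobimetinib reductions.** State Table 6 by starting dose. From 60 mg: 40 mg, then 20 mg, then discontinue. From 40 mg: 20 mg, then discontinue. Limit the two-reduction allowance in Section 8.2.4 to 60 mg starters. This also settles what counts as a reduction for the DLT definition.

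The cost is amendment wording and a site memo. The design, sample size and planned analyses do not change.
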